## 4.4 Retention

Once participants enroll in this study, the study site will make every effort to retain them for the duration of follow-up in order to minimize possible bias associated with loss-to-follow-up. A retention rate of 90% will be targeted. The study staff is responsible for developing and implementing local standard operating procedures to target this goal. Components of such procedures include:

- Thorough explanation of the study visit schedule and procedural requirements during the informed consent process, and re-emphasis at each study visit
- Thorough explanation of the importance and inter-relatedness of all the product dose and sampling phases to the overall success of the study
- Use of appropriate and timely visit reminder mechanisms (via email and/or telephone/text)
- Immediate and multifaceted follow-up (i.e. phone/text, email, and/or any other communication methods available at the disposal of site's study staff) on missed visits
- The protocol principal investigator in consultation with the site investigator will determine if research participants who fail to complete all biopsy collection sessions should be replaced. Replacement subjects would be assigned the same sampling schedule as the subject they are replacing.
- Any participant with quantifiable plasma TFV/FTC or peripheral blood mononuclear (PBMC) TFV-DP/FTC-TP concentrations at the Enrollment Visit (Visit 2) will be replaced. Participants with quantifiable plasma tenofovir/emtricitabine concentrations at Visit 2 will not proceed to the tenofovir douche administration and pharmacokinetic sampling portion of the protocol. PBMC TFV-DP/FTC-TP concentrations will be measured periodically. Participants with quantifiable TFV/DP/FTC-TP concentrations may continue to the TFV douche administration and pharmacokinectic sampling portion of the protocol, but may be replaced once the PBMC TFV-DP/FTC-TP results are available.

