Safety: To evaluate the safety of a single dose of a TFV douche when applied rectally, as measured by the number of  $\geq$ Grade 2 adverse events (AEs) as defined by the Division of AIDS Table for Grading the Severity of Adult and Pediatric Adverse Events. For the safety analysis, the number and the frequency of all adverse events (AEs) will be tabulated. A single summary outcome of this type (yes/no) can be reasonably assumed to follow a Bernoulli distribution. Assuming a true underlying rate of one or more participants experiencing AEs is between 0.01 and 0.20 in a sample of 16 YMSM, there would be a 81% chance that one or more participants might experience an AE when the true rate is at least 10% and a probability less than 15% when the true rate is no more than 1%. Unless the true rate is at least 3%, the probability of two or more subjects experiencing AEs will be quite small – less than 5%. Additional safety analyses will also tabulate the number and type of AEs observed overall, and by severity, site, and study product. AEs that lead to discontinuation of study participation will be tabulated separately.

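### With 16 participants, the chance of two or more with AEs passes 5% at a true rate of 2.27%, not 3%, and nears 8.2% just below 3%

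*Combined protocol and SAP*

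**What the plan says.** Section 9.6, under Safety, gives the operating characteristics for the primary safety outcome. The model is stated: "A single summary outcome of this type (yes/no) can be reasonably assumed to follow a Bernoulli distribution". The inputs are a sample of 16 and a span of true rates: "Assuming a true underlying rate of one or more participants experiencing AEs is between 0.01 and 0.20".

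Three probability statements follow:

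- At a true rate of 10%: "in a sample of 16 YMSM, there would be a 81% chance that one or more participants might experience an AE".
- At a true rate of no more than 1%, the chance of at least one participant with an AE is put below 15%.
- For two or more participants: "Unless the true rate is at least 3%, the probability of two or more subjects experiencing AEs will be quite small". The size is given as "will be quite small – less than 5" percent.

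No other section repeats or qualifies the third statement.

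**The concern.** The third statement bounds a probability for every true rate below 3%. With 16 participants, that probability is already above 5% at rates clearly under 3%, so the threshold and the bound do not belong together.

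Grade 2 or higher AEs are a primary endpoint (Section 2.2), and this paragraph is where the plan tells the reader what 16 participants can show about them. Someone who sees two participants with AEs could use the sentence to set aside any true rate below 3% at the 5% level. The binomial figures allow that only for rates below 2.27%. The error understates how readily two events can occur when the true rate is low.

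**Working it through.** **Inputs, all from the Safety paragraph of Section 9.6.** n = 16; one yes/no outcome per participant; p, the true per-participant rate, anywhere from 0.01 to 0.20. With participants independent, the number with an AE is Binomial(16, p).

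**Formulas.**

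- P(1 or more) = 1 − (1 − p)^16
- P(2 or more) = 1 − (1 − p)^16 − 16·p·(1 − p)^15

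**Step 1: reproduce the plan's other two figures.**

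- p = 0.10: 1 − 0.90^16 = 1 − 0.1853 = 0.8147. The plan says 81%; this agrees.
- p = 0.01: 1 − 0.99^16 = 1 − 0.8515 = 0.1485. The plan says below 15%; this agrees.

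The model and n = 16 are therefore the ones the plan used.

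**Step 2: the two-or-more probability.**

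- p = 0.02: 1 − 0.7238 − 0.2363 = 0.0399
- p = 0.025: 1 − 0.6669 − 0.2736 = 0.0595
- p = 0.03: 1 − 0.6143 − 0.3040 = 0.0818 (unrounded terms)

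| True rate | P(2 or more of 16) |
|---|---|
| 1% | 1.09% |
| 2% | 3.99% |
| 2.26% | 4.97% |
| 2.27% | 5.01% |
| 2.5% | 5.95% |
| 2.7% | 6.81% |
| 2.9% | 7.71% |
| 2.99% | 8.13% |
| 3% | 8.18% |

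Solving P(2 or more) = 0.05 numerically gives p = 2.268%.

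**Step 3: could another reading give 5% at 3%?**

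- *A different sample size.* At p = 0.03, P(2 or more) is 4.86% for n = 12 and 5.64% for n = 13, so n would have to be 12 or fewer. At n = 12, P(1 or more) at 10% is 71.8%, not 81%. The 81% fits only n = 16: it is 79.4% for n = 15 and 83.3% for n = 17.
- *A Poisson approximation with mean 16p.* At 3% it gives 8.4%.
- *Exactly two participants.* At 3% this is 7.1%.
- *Three or more participants.* This is 1.1% at 3% and reaches 5% only at 5.31%. It stays under 5% below 3%, but the plan says two or more.

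No reading that keeps two or more events and n = 16 reproduces the stated bound.

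**The case against.** The best defence is that the author worked in whole percentages. Every single rate the paragraph names is a whole percent (1%, 3%, 10%). On that grid the sentence is true: 1.1% at 1%, 4.0% at 2%, and 3% is the first value above 5%. This is probably how the sentence arose. But the text gives a continuous span of rates and no grid, and its wording takes in 2.5%, where the probability is 5.9%. The defence explains the slip without making the sentence correct.

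It can also be said that the 81% statement is loosely worded, since the chance exceeds 81% for any rate above 10%, and that it would be uneven to read one sentence strictly and the other not. That is fair, but the 81% is at least a valid lower bound for the rates it covers. The 5% figure is offered as an upper bound and is exceeded.

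The argument that the point matters little stands. The affected band is about 0.7 percentage points wide (3.0 − 2.27), and the excess is at most about 3.2 points (8.2 − 5.0). Section 9.6 plans tabulation and exact confidence intervals, Section 9.4 justifies the sample size by comparability with DREAM-01, and Sections 7.2 and 7.7 rest safety decisions on review of events. Table 4 also lists 3 participants with Grade 2 and 1 with Grade 3 AEs under Product C. Taking all 18 DREAM-01 participants as the denominator, and depending on overlap, that is 3/18 to 4/18, or 17% to 22%, far above the disputed band.

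**Conclusion.** The statement is wrong as written. For 16 participants, the probability of two or more with AEs stays below 5% only for true rates below 2.27%. Just under 3% it is close to 8.2%, about 1.6 times the stated ceiling. The sentence does hold at 1% and at 2%.

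The conclusion rests on the plan's own inputs plus independence between participants, and on reading its "Assuming a true underlying rate of one or more participants experiencing AEs is between 0.01 and 0.20" as a per-participant rate. The reproduction of the two neighbouring figures supports that reading.

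This is a minor correction to a descriptive operating characteristic. No sample size, test or stopping rule depends on it.

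**What to change.** Edit the one sentence in the Safety paragraph of Section 9.6. Either version is correct:

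- *For true rates of 2% or less, the chance that at least two of the 16 participants have an AE is below 5% (4.0% at 2%).*
- *For true rates below 3%, the chance that at least two of the 16 participants have an AE is below about 8.2%.*

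The first keeps the 5% reference and is the simpler choice. The cost is one sentence of text; the design, sample size and analyses do not change.

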DREAM-01 compared three different douche formulations including iso-osmolar Product A (220 mg TFV in 125 mL normal saline [0.9% NaCl]), iso-osmolar Product B (660 mg TFV in 125 mL normal saline), and Product C (660 mg TFV in 125 mL half-normal saline [0.45% NaCl], a hypo-osmolar formulation. Each participant received each of the 3 formulations to allow paired comparisons for safety and PK. We enrolled 18 healthy HIV-uninfected adult MSM, to identify the dose and osmolarity that achieves target colonic tissue cell TFV-DP concentrations to exceed iPrEX tissue EC90, based on levels from 4 PO TDF doses/ week. Semi-intensive sampling of plasma and PBMCs and sparse sampling of rectal fluid and colon tissue was performed. Ex vivo explant susceptibility to HIV infection was assessed via colon biopsies, and acceptability was assessed via questionnaires and in-depth interviews. A within-subject comparison of safety, PK, PD, distribution, & acceptability of 3 TFV douche formulations was conducted. 

The douche was demonstrated to be safe and well tolerated, with high acceptability to participants. All three products were generally well-tolerated. There were three Grade 3 Adverse Events (AE), one in each study phase, none of them deemed to be product related. There were a total of two AE's that were deemed product-related (rectal dryness and blood-tinged enema effluent, in a participant with history of internal hemorrhoids), and both were Grade 1 (See Table 4). Adverse events were also not dose related.

	While on Study	During Baseline	During Phase 1	During Phase 2	During Phase 3
		No Study Product	Study Product A	Study Product B	Study Product C
		(Visit 2)	(Visits 3-7)	(Visit 8-11)	(Visit 12-16)
Participants who expe	rienced an AE [3]	·		·	·
Grade 1	29	0	13	8	8
Grade 2	14	1	8	2	3
Grade 3	3	0	1	1	1
Grade 4	0	0	0	0	0
Grade 5	0	0	0	0	0
Total	46	1	22	11	12
Total # of AEs reported	d [8]		1		
Grade 1	60	0	29	10	21
Grade 2	20	1	10	2	7
Grade 3	3	0	1	1	1
Grade 4	0	0	0	0	0
Grade 5	0	0	0	0	0
Total	83	1	40	13	29

Table 4. Aggregate adverse events and	histology results from DREAM-01 (n=18)	

*Histology*. Rectal biopsies from baseline (pre-dose) and post-dose at times associated with PK and PD sampling (1, 3, 6, 24, 72, and 162 hours) and displayed in Table 5. AE refers to a scale established for evaluation of inflammatory bowel disease.

[figure not shown]

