Table 5. Rectal biopsies from baseline (pre-dose) and post-dose at times associated with PK and PD sampling (1, 3, 6, 24, 72, and 162 hours)

Product	Post- Dose Hours	N	Grade		Grade Epithelial Denudation		Lamina Propria Hemorrhage	
			Median (IQR)	p value*	Median (IQR)	p value	Median (IQR)	p value
Baseline	pre-dose	21	0.0 (0.0, 1.0)	-	0.0 (0.0, 1.0)	-	1.0 (0.0, 1.0)	-
Α	1-6	21	1.0 (0.0, 1.0)	0.79	0.0 (0.0, 1.0)	1.00	1.0 (0.0, 1.0)	1.00
	24	6	0.5 (0.0, 1.3)	1.00	0.0 (0.0, 2.0)	0.31	1.0 (1.0, 1.0)	0.50
	72	8	0.5 (0.0, 1.0)	1.00	0.0 (0.0, 0.0)	0.63	0.0 (0.5, 1.0)	1.00
	168	6	0.0 (0.0, 0.3)	1.00	0.0 (0.0, 0.3)	1.00	1.0 (0.0, 1.0)	1.00
В	1-6	19	1.0 (0.0, 1.0)	0.31	0.0 (0.0, 0.0)	0.79	1.0 (0.0, 1.0)	0.51
	24	6	1.0 (0.8, 1.0)	0.75	1.0 (0.0, 1.0)	0.50	1.0 (0.0, 1.0)	0.63
	72	8	0.5 (0.0, 1.0)	1.00	0.0 (0.0, 0.0)	1.00	1.0 (0.0, 1.0)	1.00
	168	5	1.0 (0.0, 1.0)	1.00	0.0 (0.0, 0.5)	0.63	1.0 (1.0, 1.0)	1.00
С	1-6	16	0.0 (0.0, 1.0)	0.69	0.0 (0.0, 0.8)	0.59	1.0 (1.0, 1.0)	0.22

24	6	1.0 (1.0, 1.3)	0.63	0.5 (0.0, 1.3)	1.00	1.0 (0.8, 1.0)	0.25
72	6	0.5 (0.0, 1.0)	1.00	0.0 (0.0, 1.0)	1.00	0.5 (0.0, 1.0)	1.00
168	5	0.0 (0.0, 0.5)	1.00	0.0 (0.0, 0.0)	1.00	1.0 (1.0, 1.0)	1.00

*Acceptability*. All three DREAM Products were found acceptable to participants, including Product C, the hypo-osmolar, high dose formulation to be used in this trial. Participants indicated high baseline anticipated likelihood of using the products before receptive anal intercourse for HIV prevention, with 15/17 participants indicating at baseline that they would be likely or very likely to use such products.

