# 1.7 DREAM ATN Design Rationale

According to our working target product profile and our clinical niche as an on demand PrEP product, the TFV douche is being developed to provide protective concentrations in colon tissue cells for a similar duration as that achieved using the on demand oral F/TDF 2+1+1 regimen demonstrated equally effective with daily F/TDF in Ipergay. Therefore, sampling for PK and safety will occur over 72 hours based on our model-based PK estimates. In addition, we intend to establish the congruence of PK between adult in the DREAM studies and the YMSM population to be recruited in this DREAM ATN protocol. Accordingly, we propose a slightly shorter total PK sampling duration (3 days) when compared to DREAM-01 (7 days). This

will enable documentation of concentrations throughout the first day when DREAM-01 indicated sustained concentrations well above target concentrations in colon tissue cells as well as the initial decay in concentration that occurs between 24 and 72 hours when colon tissue TFV-DP median concentration falls nearer to the 4 dose per day target concentration.

To achieve these goals, blood (plasma and cells), colon tissue (tissue homogenate and cells), and rectal fluid will be collected using a relatively sparse sampling scheme that balances a desire for rich PK data collection and feasibility. Altogether, each participant will have 5 pharmacokinetic blood samples, 2 rectal fluid samples, and 2 biopsy sessions (up to eight pinch biopsies at baseline and 20 pinch biopsies at one time point following dosing) for the enema product studied. The total number of pinch biopsies collected following enema formulation dosing (n=20) in adolescents is well below the number collected in adult participants (n=120) in DREAM-01.

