Pre-dose baseline visit tissue biopsies, plasma and blood will be collected to provide comparisons for pre and post dosing in challenge studies and to establish that no oral PrEP is being taken, respectively. After a single dose of the TFV douche (previously referred to as Product C in DREAM-01) we will collect samples at predose, 1, 6, 24, and 72 hours to establish the early rate of increase, peak concentrations, and initial decay of TFV and TFV-DP in all matrices. Plasma and PBMC will be collected from each participant at all of these timepoints. Rectal fluid sampling is partially destructive of local matrix, so, we are planning only two rectal fluid samples per participant in the first 72 hours). Colon tissue biopsies will be collected at each of these times, but each participant will be assigned to only one of these post-dose biopsy times, using a sparse sampling approach and population PK analysis. Aggregate estimates for PK parameters will be used. Non-linear mixed effect modeling will be attempted, but the total sample size may be insufficient to generate robust PK parameter estimates.

Note: Gastrointestinal (GI) sampling procedures for PK/PD assessment (e.g. anoscopy, flexible sigmoidoscopy with biopsy) will not be conducted in participants less than age 18. Participants older than age 18 will be prioritized to undergo GI assessment, but if this adversely impacts accrual feasibility, sample collection may be limited to plasma/PBMC only.

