Pharmacokinetics: To characterize the systemic and compartmental pharmacokinetics of a TFV douche following rectal application, as measured by TFV concentrations in plasma, rectal fluid and rectal mucosal tissue homogenates and cells. Pharmacokinetic parameters will be compared to data from studies using rectal dosing of TFV in DREAM-01 and other oral TFV dosing studies in adults, which also included colorectal biopsies. Pharmacokinetics in blood plasma and PBMCs, colon tissue homogenate and cells, and rectal fluid for the TFV-based douche will be evaluated after rectal administration. The primary analysis will use noncompartmental methods to estimate pharmacokinetic parameters, including peak concentration (Cmax, time to peak concentration ( $T_{max}$ ), area under the matrix concentration-time curve from 0 to infinity ( $0 \rightarrow \infty$ ), and terminal elimination half-life. For sparsely sampled matrices (colon tissue homogenate, colon tissue cells, and rectal fluid), we will use population PK methods to build PK models describing individual PK parameter estimates and typical values for the population along with significant covariates (possibly weight, age, pharmacogenetics, creatinine clearance). Tenfovir and TFV-DP assays will be performed by the Clinical Pharmacology Analytical Laboratory (CPAL) at Hopkins and are validated following FDA bioanalytical guidance and approved by an NIH-cross network Clinical Pharmacology Quality Assurance (CPQA) program before used in clinical studies. Primary PK analyses will be testing for (1) differences in PK measures between the two age groups (Kruskal-Wallis) and (2) comparison with DREAM-01 PK results.

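### Plasma and PBMC Cmax and Tmax from samples at 1, 6, 24 and 72 h are to be compared with DREAM-01 values from a denser schedule, with no rule putting both studies on the same times

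*Combined protocol and SAP*

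**What the plan says.** Section 9.6 (Pharmacokinetics): "The primary analysis will use noncompartmental methods to estimate pharmacokinetic parameters, including peak concentration". Tmax, AUC from zero to infinity and terminal half-life follow in the same list. The section also says "Pharmacokinetic parameters will be compared to data from studies using rectal dosing of TFV in DREAM-01", and ends by naming two primary PK analyses: the two age groups against each other, and comparison with DREAM-01. For colon tissue homogenate, colon tissue cells and rectal fluid it assigns population PK methods.

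Section 1.7 on DREAM ATN sampling: "we will collect samples at predose, 1, 6, 24, and 72 hours to establish the early rate of increase, peak concentrations". It describes the scheme in these terms: samples "will be collected using a relatively sparse sampling scheme that balances a desire for rich PK data collection and feasibility". Table 10 sets the blood windows at 1 h ± 15 min and 6 h ± 60 min, so no blood is planned between 1.25 h and 5 h.

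Section 1.6 on DREAM-01: "Semi-intensive sampling of plasma and PBMCs and sparse sampling of rectal fluid and colon tissue was performed". The Table 5 caption in the same section gives biopsies "post-dose at times associated with PK and PD sampling (1, 3, 6, 24, 72, and 162 hours". DREAM-01 plasma and PBMC clock times are not listed.

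Nothing in section 9 restricts the comparison to shared times, recomputes DREAM-01 on the DREAM ATN times, or specifies a joint model.

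**The concern.** Noncompartmental Cmax is the largest observed value, and Tmax is the time at which it was observed. Both depend on when samples were drawn. If DREAM-01 sampled at these four times and at others between 1 and 6 h, its Cmax will tend to be higher than that of DREAM ATN for the same underlying curve. A 3 h peak will be recorded as 3 h in one study and as 1 or 6 h in the other. Enrolling more participants does not remove this.

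Section 1.6 gives the purpose of the comparison as establishing PK equivalence across adolescents, young adults and adults. An artefact of the schedule could suggest a lower or differently timed systemic peak in YMSM where none exists, or hide a peak that is truly higher in YMSM. The issue is separate from stopping at 3 days rather than 7, which bears on AUC to infinity and half-life.

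**Working it through.** The plan gives no figure for the effect of the sampling schedule, so there is none to reproduce.

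**Inputs from the documents.** DREAM ATN times 1, 6, 24 and 72 h (section 1.7); a 3 h PK/PD time in DREAM-01 (Table 5 caption); 16 and 18 participants and a two-sided 5% level (section 9.4); rank tests (section 9.6).

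**Assumed, because the documents do not give them.** One-compartment first-order absorption, true time of peak, half-life, between-participant variability and residual error.

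**Step 1: direction.** If the DREAM ATN times are a subset of the DREAM-01 times, then for any one profile max{C(1), C(6), C(24), C(72)} ≤ max{C(1), C(3), C(6), C(24), C(72)}. Any Cmax bias therefore lowers the YMSM value. Tmax can move either way.

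**Step 2: one curve without noise.** C(t) ∝ [ka/(ka − ke)]·[exp(−ke·t) − exp(−ka·t)], with ke = ln 2 / half-life and Tmax = ln(ka/ke)/(ka − ke). Take half-life 6 h and true Tmax 3 h:

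- ke = 0.693/6 = 0.1155 per h. Solving the Tmax equation gives ka = 0.730 per h, so ka/(ka − ke) = 1.188.
- C(1) = 0.486, C(3) = 0.707, C(6) = 0.579, in units of the dose term.
- DREAM ATN records 0.579 at 6 h. A schedule with a 3 h sample records 0.707 at 3 h. The ratio is 0.579/0.707 = 0.82.

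The same calculation for other settings:

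| True Tmax | Half-life 6 h | 12 h | 24 h | 48 h |
|---|---|---|---|---|
| 1.5 h | 1.00 | 1.00 | 1.00 | 1.00 |
| 2 h | 0.91 | 0.93 | 0.94 | 0.96 |
| 2.5 h | 0.78 | 0.86 | 0.92 | 0.96 |
| 3 h | 0.82 | 0.89 | 0.94 | 0.97 |

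The noise-free Cmax effect of a missing 3 h sample disappears when the peak is at or before 1.5 h.

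**Step 3: two identical populations, 16 against 18, Wilcoxon rank sum at two-sided 5%, only 3 h added to DREAM-01.**

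| Assumptions | Cmax ratio | False rejection, Cmax | False rejection, Tmax |
|---|---|---|---|
| Peak 2–3 h, half-life 2–17 h, log SD of exposure 0.5 | 0.83–0.93 | 7–15% | 7–76% |
| Peak 0.75–3 h, half-life 4–48 h, 40% CV on exposure and absorption, about 20% CV on elimination, 20% residual error | 0.82–0.96 | 5–21% | 7–42% |
| Peak 0.5–1 h, half-life 4–17 h, 20% residual error | 0.93–0.98 | 4–7% | inflation persists |

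With residual error, the maximum of more samples is higher even when the extra sample is past the peak, so the ratio stays slightly below 1 for early peaks. For example, with a 1 h peak and 6 h half-life the Cmax ratio is 0.95 and Cmax rejection 5%, but Tmax rejection is 37%.

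**Step 4: both studies reduced to 1, 6, 24 and 72 h.** In the four settings rerun under the second set of assumptions, the Cmax ratio was 0.998 to 1.001, Cmax rejection about 4 to 5%, and Tmax rejection at most about 5%. Under the first set, same-schedule rejection was 4.5 to 5.4% for Cmax and 2 to 6% for Tmax.

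**Sensitivity.** With an assumed plasma schedule of 0.5, 1, 2, 3, 4, 6, 12, 24, 48, 72 and 168 h for DREAM-01, the Cmax ratio falls to 0.74–0.87 and false rejection rises to 14–46% (Cmax) and 9–57% (Tmax). That schedule is an assumption, so these figures show only how the problem grows with sampling density.

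**The case against.** A reader might infer that this undermines the primary PK endpoint and the bridge to adults. The documents do not support that. The primary PK endpoint (section 2.2) is colon tissue MMC TFV-DP concentration, and section 1.3 places the adult–YMSM congruence in colon tissue cells. Each participant has one post-dose biopsy session, so no individual tissue Cmax or Tmax exists, and section 9.6 assigns tissue and rectal fluid to population PK. What remains for tissue is conditional: section 1.7 plans aggregate estimates and warns that modelling may not be robust, and a peak read from an aggregate profile would have the same fault.

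Nor can it be said that DREAM-01 drew plasma at 3 h, or that the plan has chosen to compare mismatched schedules. The 3 h time is documented for biopsies. On the method of comparison section 9.6 is silent: it names Kruskal-Wallis for the age groups and Wilcoxon for test formulations, but no test for the DREAM-01 comparison. The simulated rejection rates therefore assume that a rank test is used.

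The peak time is also assumed. The DREAM-01 tissue results in section 1.6 show concentrations above target within 1 h and sustained over 24 h, which does not suggest a sharp peak at 2–3 h. That is tissue rather than plasma, but if plasma also peaks early the Cmax effect is close to nominal. The Tmax effect is less easily dismissed, although its range is too wide to be a forecast.

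Finally, this is an exploratory study that openly chose sparse sampling. That argues for a small change, not for none.

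**Conclusion.** The point holds for plasma TFV and PBMC TFV-DP, where each participant has a full profile. As written, the plan allows a comparison in which identical populations differ in Cmax and Tmax because of sampling times alone. The direction for Cmax follows without any pharmacokinetic model, provided the DREAM-01 times include those used here.

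The size rests on assumed pharmacokinetics with only a 3 h sample added: a Cmax ratio of about 0.82 to 0.98, false rejection of about 5 to 21% for Cmax (near nominal if the peak is at or before about 1.5 h), and about 7 to 76% for Tmax. On a common schedule neither materially exceeds 5%. The change is worth making before results are seen, because choosing the schedule afterwards could alter the conclusion.

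**What to change.** Add to section 9.6 (Pharmacokinetics):

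- The inferential comparison of plasma and PBMC Cmax and Tmax with DREAM-01 uses DREAM-01 Product C parameters recomputed at the nominal times common to both studies (1, 6, 24 and 72 h where available). If DREAM-01 lacks one of these, both studies are reduced to the times they share.
- Concentrations at each common time are shown beside the parameters. Full-schedule DREAM-01 values are reported descriptively.
- Any peak read from an aggregate tissue or rectal fluid profile uses the same common times in both studies.
- The test for this comparison is named, and the DREAM-01 plasma and PBMC sampling times are listed.

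A joint population model with a study effect would keep all the DREAM-01 data and could be added as a supporting analysis, subject to the sample-size warning in section 1.7.

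The cost is a re-run of existing DREAM-01 data, with no new samples, visits or participants. The downside is that DREAM-01's extra samples go unused in this one comparison, and a real difference between 1 and 6 h would not be seen by it.

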*PK-PD*. Plasma concentration vs. time course indicates median TFV concentration at all times after the TFV douche fall below the median steady-state plasma TFV trough concentrations associated with 4 doses per week (HPTN 066 as reference population) (Figure 2). TFV-DP in colon tissue cells extracted from colon biopsies vs. time. TFV 660 mg dose, half-normal saline (HNS) achieves similar peak TFV-DP concentrations as TFV 660 mg in normal saline (NS) formulation, but the rate of rise is faster based on data one hour after dosing. All products provide concentrations within 1 hour after dosing that exceeds the target concentration, sustained across the first 24 hours before falling to levels at (TFV 220 mg NS) or several fold above (TFV 660 mg, NS or HNS) target concentrations by 3 days post-dose. This decline is faster than the TFV-DP decay previously observed in PBMCs. Viral p24 antigen (accumulated over 14 days in the tissue supernatant) from explants collected after *in vivo* TFV douche dosing and *ex vivo* biopsy HIV challenge in tissue culture. The median p24 antigen declines to very near lower limit of assay quantitation by 1 hour after dosing where it remains until increasing back nearly to baseline values by 72 hours, generally mirroring the TFV-DP colon tissue cell TFV-DP pattern. Compared to baseline, the group of all biopsies collected 1-24 hours after dosing reduced HIV viral replication in *ex vivo* colon tissue explants by median (IQR) 0.77  $\log_{10}(0.20, 0.81)$  (p<0.01).

**Figure 2**. PK and PD readouts from the DREAM-01 clinical study. All values are median and interquartile range. *Upper Left Panel*. Plasma concentration vs. time course with 4 oral F/TDF doses per week as reference (HPTN 066 as reference population). *Upper Right Panel*. TFV-DP in colon tissue cells extracted from colon biopsies vs. time. Same TFV-DP 4 dose per week

reference for oral F/TDF dosing reference as for plasma. *Lower Right Panel*. Viral p24 antigen (accumulated over 14 days in the tissue supernatant) from explants collected after *in vivo* TFV douche dosing and *ex vivo* biopsy HIV challenge in tissue culture.

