YMSM will then receive a single dose of TFV douche at the research unit, and, asked to retain the douche without defecation for 5 minutes, if possible. Subsequently, participants will be instructed on how to expel the douche contents. The amount of time that the douche was retained and the volume of expelled effluent will be measured. Post-dose observations and data collection will follow at 1, 6, 24, and 72 hours, using a sparse PK sampling design in which plasma and peripheral blood mononuclear cells (PBMC) are collected at each designated time. Participants are randomized to only one time point for flexible sigmoidoscopy with rectal biopsies at either 1, 6, 24, or 72 hours after dosing (thus, providing 4 subjects at each time point). Anoscopy, with rectal fluid collection will occur pre-dose, 1, 6, 24 or 72 hours after dosing to coincide with the time of each participant's flexible sigmoidoscopy. Microbiome specimens will be collected via anoscopy pre-dose and at 24 hrs post-dose.

Between sampling windows, YMSM will complete a web-survey examining their perceived reactions and comfort using the study douche, factors influencing product use in the future, and comfort with the trial procedures. The survey will be administered after dosing but scheduled not to interfere with other study assessments. Sampling for safety, PK, PD, and acceptability assessments will be collected according to the schedule of events. Phase I Trial participants will complete in an IDI as part of their termination visit.

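### AUC to infinity and terminal half-life from 72 h of sampling are set against 7-day DREAM-01 data, with no common window and no report of the share extrapolated

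*Combined protocol and SAP*

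**What the plan says.** Section 9.6 (Pharmacokinetics) states: "The primary analysis will use noncompartmental methods to estimate pharmacokinetic parameters". The parameters it lists are peak concentration, time to peak, "area under the matrix concentration-time curve from 0 to infinity" "and terminal elimination half-life". The next sentence sets a different method for some matrices: "For sparsely sampled matrices (colon tissue homogenate, colon tissue cells, and rectal fluid), we will use population PK methods". The paragraph ends by naming two primary PK analyses: a test between the two age groups and a comparison with the DREAM-01 results.

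The sampling is in section 9.1: "Post-dose observations and data collection will follow at 1, 6, 24, and 72 hours". Section 1.7 says that this is 3 days of sampling against 7 in DREAM-01, and describes the last interval as "the initial decay in concentration that occurs between 24 and 72 hours". On colon-cell TFV-DP in DREAM-01, section 1.6 says that levels were above target within an hour, "sustained across the first 24 hours before falling to levels" that, for the 660 mg products, were still several times the target at 3 days. It adds that this decline is faster than that seen earlier in PBMCs.

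Section 9.6 names no AUC 0-72 h, no truncation of the DREAM-01 data, no rule for choosing the terminal slope and no limit on the extrapolated share.

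**The concern.** AUC to infinity is the observed area plus a tail equal to the last concentration divided by the terminal slope. Both pieces of that tail depend on when sampling stops. Here they come from an interval that the protocol itself treats as the start of the decline; in DREAM-01 they come from samples up to four days later. If a slower phase follows 72 h, this trial will report a shorter half-life and a smaller AUC to infinity than DREAM-01 would for the same true profile.

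The trial is meant to supply a PK bridge from adults to young MSM (section 1.6). A gap in half-life or total exposure produced by the schedule could be read as a difference between populations, and a real difference could be masked.

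**Working it through.** The documents give no half-life, AUC or extrapolated share, so there is no stated figure to reproduce. Inputs from the documents: last sample at 72 h here (section 9.1); 7 days, taken as 168 h, in DREAM-01 (section 1.7; Table 5 also uses 168 h). All half-lives below are assumptions.

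**1. One-compartment decline.** Share of AUC beyond T = exp(-ln 2 x T / half-life).

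| Half-life (h) | Beyond 72 h | Beyond 168 h |
|---|---|---|
| 20 | 8% | 0.3% |
| 24 | 12.5% | 0.8% |
| 48 | 35% | 9% |
| 72 | 50% | 20% |

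The share beyond 72 h reaches 20% at a half-life of 72 x ln 2 / ln 5 = 31 h.

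**2. Colon TFV-DP from the protocol's wording.** Section 1.6 puts colon levels more than 10-fold above the reference and several-fold above target at 72 h. Assume a plateau P of 10 or 20 times target up to 24 h, then log-linear decline to c = 2 to 5 times target at 72 h. Then:

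- slope k = ln(P/c)/48
- AUC 0-72 = 24P + (P - c)/k
- tail = c/k

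At the upper end (P = 10, c = 5): k = 0.01444 per h, half-life 48 h, AUC 0-72 = 240 + 346.2 = 586.2, tail 346.2, share 346.2/932.4 = 37%. At the lower end (P = 20, c = 2): k = 0.04797, half-life 14.4 h, AUC 0-72 = 480 + 375.2 = 855.2, tail 41.7, share 41.7/896.9 = 5%. In between, P = 10 with c = 2 or 3 gives 11% or 19%. Beyond 168 h the share is 9% at most.

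**3. Same true curve, two schedules.** Five illustrative curves C(t) = (1 - w) x 2^(-t/f) + w x 2^(-t/s) were analysed by log-trapezoid, with the slope from the last two samples. Schedules: 1, 6, 24, 72 h, and 1, 3, 6, 24, 72, 168 h (assumed for DREAM-01).

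| f, s (h), w | Half-life: 72 h vs 168 h schedule | Ratio of AUC to infinity | Ratio of AUC 0-72 h |
|---|---|---|---|
| 8, 48, 0.2 | 27.6 vs 47.3 | 0.91 | 1.00 |
| 12, 72, 0.2 | 28.7 vs 63.9 | 0.84 | 1.00 |
| 12, 96, 0.2 | 32.3 vs 84.0 | 0.76 | 1.00 |
| 15, 150, 0.1 | 25.4 vs 82.4 | 0.77 | 1.00 |
| 20, 100, 0.3 | 39.3 vs 72.4 | 0.81 | 1.00 |

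The ratios are the 72 h schedule over the 168 h schedule. AUC to infinity falls by 9% to 24% from the schedule alone, while AUC 0-72 h agrees even though only one schedule has a 3 h sample.

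**4. Slope noise.** If a slope rests on the 24 h and 72 h samples only, with an assumed residual log-SD of 0.3, its SD is 0.3 x sqrt(2)/48 = 0.0088 per h. Against a slope of 0.0144 (half-life 48 h) that is a CV of about 61%, and about 5% of slopes would be zero or negative, leaving AUC to infinity undefined.

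**The case against.** The strongest reply is that the endpoints do not need extrapolation. The primary PK endpoint in section 2.2 is colon-cell TFV-DP concentration from 1 to 72 h, the PK hypothesis in section 9.3 covers the same period, and the secondary endpoints are concentration summaries. AUC to infinity is one of four listed parameters, and section 1.7 discloses and justifies the shorter sampling. This stands: the primary endpoint is not compromised. The listed parameters still feed a primary comparison with DREAM-01.

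A second reply is that colon tissue and rectal fluid go to population PK rather than individual noncompartmental analysis. That is correct, but a model fitted to data ending at 72 h must also extrapolate to reach infinity, and section 1.7 warns that the sample may be too small for robust model estimates.

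Three stronger readings are tempting and should not be drawn:

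- **That a large extrapolated share is established.** It is not. With no half-life given, the share is below 20% for any one-compartment half-life under 31 h. Half-lives of 72 h or more sit badly with a colon level that section 1.7 says moves nearer to target by 72 h.
- **That the window mismatch biases the age-group comparison.** Both age groups share one schedule, so only slope noise applies there.
- **That every terminal slope rests on two points.** The 24 h plateau is described for colon cells, where each participant has one post-dose biopsy and no individual slope exists. For plasma and PBMC the documents do not say when the terminal phase starts, so the 6 h sample may contribute.

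**Conclusion.** The point holds for the DREAM-01 comparison of AUC to infinity and half-life. These quantities depend on how long sampling lasts, the two studies differ (3 against 7 days), and section 9.6 provides nothing to align them or to show how much is extrapolated.

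The size depends on the matrix. It is small where the half-life is 20 h or less and roughly 5% to 37% for colon TFV-DP, reading several-fold as 2 to 5 times target and the plateau as 10 to 20 times. It would be higher for PBMC TFV-DP, by an amount the documents do not allow one to fix. The 9% to 24% shortfall in AUC to infinity comes from illustrative curves with a slow second phase; if decline is truly one-compartment, the slope is unbiased and the cost is mainly imprecision. This is a worthwhile and inexpensive correction to the analysis text, not a flaw in the primary endpoint.

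**What to change.** In section 9.6:

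- Make AUC 0-72 h the exposure measure for the DREAM-01 comparison, computed over the same 0-72 h window in the DREAM-01 Product C data.
- As a check, repeat it in DREAM-01 using only the shared 1, 6, 24 and 72 h times, since DREAM-01 biopsies were also taken at 3 h.
- For colon tissue and rectal fluid, use a model-based or composite-profile AUC 0-72 h. With at most 4 participants planned per biopsy time, and no such sampling under age 18, its precision will be limited and should be reported.
- Report AUC to infinity and half-life descriptively only, by matrix, with the percentage extrapolated and the samples used for the slope.

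This needs no new visits or samples. It costs analysis-plan wording and re-truncation of the DREAM-01 data, to which the planned comparison already presupposes access. The downside is that total exposure is no longer compared formally. In return, the exposure measure matches the 72 h limit of the primary endpoint.
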